3.2 Secondary Objectives and Hypotheses

1. **Objective:** To determine the effect of nivolumab and Metformin combination on clinical outcomes, progression free survival and overall survival, and biochemical response (CEA).

Hypothesis: Metformin plus nivolumab will affect overall response rate, progression free survival, overall survival.

2. **Objective:** To compare the effect of nivolumab and metformin combination on immune and metabolic biomarkers in the tumor microenvironment and systemic circulation (pre and post treatment paired biopsies required).

Hypothesis: Metformin plus nivolumab will change the immune profile in the peripheral blood as well as the tumor microenvironment.

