- h. Paired biopsies (biopsy#1) will be obtained at baseline from all 28 patients within 28 days before Cycle 1 day 1 after consent is signed, subject #1-9, 19-23 (14 patients in total) will get post treatment biopsy (biopsy#2) cycle 1 Day 1 (same day or up to 5 days later) nivolumab will be given after biopsy#2 (same day or up to 5 days later) and subject# 10-18, 24-28 (14 patients in total) will get post treatment biopsy (biopsy#2) C1 Day 15 (same day or up to 5 days later). Most accessible metastatic disease tumor site will be biopsied by Emory Interventional Radiology. Same site will be biopsied at biopsy#1 and biopsy#2. 3 core biopsies will be obtained each time. If a patient undergoes biopsy#1 and refuse biopsy#2 this subject will be replaced. Subjects continue metformin on days of biopsy#2, and take metformin preferably 2 hours prior to the biopsy.

- i. Correlative samples will be collected at baseline, cycle 1 day 1, cycle 1 day 15, Cycle 3 Day 1 and at progression. Analysis will include phenotypic and functional analysis of T and myeloid cell subsets.

- j. Must be within 72 hours of the study drug

*Unless otherwise specified

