8.1.3.1 Tumor Tissue Collection and Correlative Studies Blood Sampling

Paired biopsies (biopsy#1) will be obtained at baseline from all 28 patients within 28 days before Cycle 1 day 1 after consent is signed, subject #1-9, 19-23 (14 patients in total) will get post treatment biopsy (biopsy#2) cycle 1 Day 1 (same day or up to 5 days later) and subject# 10-18, 24-28 (14 patients in total) will get post treatment biopsy (biopsy#2) C1 Day 15 (same day or up to 5 days later). Most accessible metastatic disease tumor site will be biopsied by Emory Interventional Radiology. Same site will be biopsied at biopsy#1 and biopsy#2. We don't believe biopsy site bias the study as any metastatic site which is deemed safe and accessible can be biopsied. 3 core biopsies will be obtained each time. If a patient undergoes biopsy#1 and refuse biopsy#2 this subject will be replaced. The obtained tissues will be handled in the following way:

- 1) RNAlater for RNA stabilization and tissue storage
- 2) Formalin-fixed paraffin block with one cut H&E stained slide
- 3) Liquid nitrogen frozen tissue in cryo-preservation vials

All collected tissues are stabilized and stored in -80°C freezers (RNAlater stabilized, OCT embedded, short term storage) or the vapor phase of a liquid nitrogen freezer (long term storage) in single use aliquots. All FFPE tissue blocks are stored in a climate-controlled storage room that is temperature (less than 27°C) and humidity controlled.

Tissue will be evaluated using IHC or immunofluorescence to measure relevant immune markers (i.e. CD3, CD4, CD8, CD163, PD-1, PD-2, PDL-1, MIF, TAM and stromal/ vascular markers). When sufficient quantities of fresh tissue is available, it will also be dissociated and flow cytometry will be used to determine the phenotypic characteristics of cell populations in the tumor microenvironment. Tissue will be preserved for future exploratory studies including genomic profiling.

Peripheral blood samples

Approximately 20 mL of peripheral blood will be collected prior to initiation of study therapy (at baseline), cycle 1 day 1, cycle 1 day 15, Cycle 3 Day 1 and at progression. The peripheral blood mononuclear cells will be isolated from these samples and stored in -80°C freezers until analysis. Samples will be evaluated for:

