- i. Determine whether there are phenotypic changes in of T-cell or myeloid cell surface markers (including co-stimulatory/immune checkpoint molecules) in PBMCs after treatment. Samples will be collected at baseline, cycle 1 day 1, cycle 1 day 15, Cycle 3 Day 1 and at progression.
- ii. Determine whether functional changes are evident in PBMCs in response to treatment and whether these data correlate with clinical outcome measures. Samples will be collected at baseline and week 10th. Pending quantity of cells a variety of assays may be performed, including but not limited to intracellular cytokine production and expression of CD107.

Shipping and handling instructions

After appropriate processing, the blood samples, tissue blocks, slides or frozen tissue samples will be sent to:

[name] Laboratory
[name]
[name]
Winship Cancer Institute of Emory University
[name]

On the day that the specimens are to be shipped, notify [name] at [contact], and [name] at [contact] of the pending specimen shipments. Include the Fed-Ex tracking number in the email.

Research blood contact Information:

[name]. [contact]
[name]., MPH [contact]

Methods and materials per Lab Manual**Table 5 Laboratory Tests**

| Hematology | Chemistry | Urinalysis | Other |
|------------------------------|----------------------------------|---|--|
| Hematocrit | Albumin | Blood | Serum β -human chorionic gonadotropin† |
| Hemoglobin | Alkaline phosphatase | Glucose | (β -hCG)† |
| Platelet count | Alanine aminotransferase (ALT) | Protein | PT (INR) |
| WBC (total and differential) | Aspartate aminotransferase (AST) | Specific gravity | aPTT |
| Red Blood Cell Count | Lactate dehydrogenase (LDH) | Microscopic exam (If abnormal) | Total triiodothyronine (T3) |
| Absolute Neutrophil Count | Carbon Dioxide ‡ | results are noted | Free tyroxine (T4) |
| Absolute Lymphocyte Count | (CO_2 or bicarbonate) | Urine pregnancy test † | Thyroid stimulating hormone (TSH) |
| | Calcium | | |
| | Chloride | | Blood for correlative studies |
| | Glucose | | |
| | Phosphorus | | |
| | Potassium | | |
| | Sodium | | |
| | Magnesium | | |
| | Total Bilirubin | | |

| Hematology | Chemistry | Urinalysis | Other |
|------------|--|------------|-------|
| | Direct Bilirubin (If total bilirubin is elevated above the upper limit of normal) | | |
| | Total protein | | |
| | Blood Urea Nitrogen | | |

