10.2 Statistical and Analytical Plans

Summary statistics will be presented for all safety, efficacy and biomarker parameter analyses. The purpose of these analyses is hypothesis generating. Various exploratory statistical tests may be applied to data generated from this trial to generate hypotheses to be tested in subsequent trials. In general, data for continuous parameters will be presented using descriptive statistics including sample size, mean, and median; standard deviation; and minimum and maximum. Categorical parameters be displayed using counts and percentages. Toxicities will be presented as worst toxicity per patient and will be reported as percent toxicity.

Objective response rate will be calculated as proportion (Responders/Total patients) along with 95% confidence intervals using the Clopper-Pearson method. Chi-square test or Fisher's exact test will be used to compare the efficacy in term of response rate, biochemical response (CEA) between the different groups stratified by biomarkers or other factors, respectively. Logistics regression

model will be further employed to test the adjusted effect of biomarkers on the response rate after adjusting for other clinical factors and demographic factors.

For progression free survival, progression or death from any cause will be defined as the event. Patients will be censored at time of last follow-up. For overall survival, death from any cause will be defined as the event. Patients will be censored at time of last follow-up. Overall survival (OS) and progression free survival (PFS) rates of two patient groups stratified by response or other factors will be estimated with the Kaplan-Meier method and compared between different groups using the log-rank test, respectively. The PFS and OS of each patient group at specific time points, such as 6 months, 1 year, 3 year, and 5 year, etc. will be also estimated alone with 95% CI. Cox proportional hazards models will be further used in the multivariable analyses to assess adjusted effect of response on the patients' OS and PFS after adjusting for other factors. Interaction terms between these factors will also be tested for statistical significance. The proportional hazards assumption will be evaluated graphically and analytically with regression diagnostics. Violations of the proportional hazards assumptions will be addressed by use of time-dependent covariates or extended Cox regression models.

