For the biomarker study, descriptive statistics will be first used to summarize biomarker endpoints, including analyses of tumor biopsies. Biomarker data will also be displayed graphically, where appropriate. Depending on whether data is normally distributed, t-test or Wilcoxon rank sum test will be used to compare each biomarker between any two groups stratified by response or other factors, respectively. General linear model (GLM) will be used to compare each biomarker between responders and nonresponders with and without adjusting for other factors. Logistics regression model will be further employed to test the adjusted effect of biomarker on the response rate after adjusting for other factors.

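### Secondary objective 2 asks for within-patient biomarker change, but section 10.2 names only between-patient tests, and the biopsy #1 window runs into the metformin lead-in

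*Combined protocol and SAP*

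**What the plan says.** **The question.** Section 3.2 sets the hypothesis for secondary objective 2: "Metformin plus nivolumab will change the immune profile in the peripheral blood as well as the tumor microenvironment". It requires biopsies before and after treatment. Section 8.1.3.1 has the same site biopsied both times, and one stated aim for the blood samples is "Determine whether there are phenotypic changes in of T-cell or myeloid cell surface markers" after treatment.

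**The tests.** The biomarker paragraph of 10.2 begins with descriptive statistics and graphs. It then names three analyses:
- a "t-test or Wilcoxon rank sum test will be used to compare each biomarker between any two groups stratified by response or other factors";
- a model: "General linear model (GLM) will be used to compare each biomarker between responders and nonresponders";
- logistic regression of response on the biomarker.

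The efficacy paragraph of 10.2 adds chi-square or Fisher tests of response between biomarker groups. A general sentence leaves room for more: "Various exploratory statistical tests may be applied to data generated from this trial". Change from baseline appears in section 10 only for safety laboratory values (10.6.2).

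**The biopsy schedule.** Biopsy #1 "will be obtained at baseline from all 28 patients within 28 days before Cycle 1 day 1 after consent is signed" (8.1.3.1; the same window is in 8.1.5.1 and calendar footnote h). Biopsy #2 is due at C1D1 in subjects 1-9 and 19-23, and at C1D15 in subjects 10-18 and 24-28. For the first group footnote h says that "nivolumab will be given after biopsy#2 (same day or up to 5 days later". Table 1 in 6.1.1 and footnote c start metformin on Day -14. The baseline blood, by contrast, "will be collected prior to initiation of study therapy (at baseline").

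**The concern.** The question is about change within a patient, while the named tests contrast one set of patients with another. Run as written, 10.2 would yield no test of objective 2, although every patient is asked for two biopsy sessions of three cores each. The response-based tests also depend on having responders, in a disease where the plan itself expects few on nivolumab alone.

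Two features of the sampling add to this. Biopsy #2 reflects metformin alone in one half of the patients and the combination in the other half, and section 10 does not say whether the halves are pooled or kept apart. And if a biopsy #1 were taken during the lead-in, the baseline would already carry some metformin effect. That would tend to shrink the measured change, most of all in the C1D1 cohort, whose only exposure is the two-week lead-in.

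**Working it through.** The plan states no power, alpha or effect size for biomarkers, so there is no figure of its own to reproduce. I assumed two-sided 5% tests and 80% power throughout.

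**1. What the response-based tests would have to work with.** Inputs from 10.1: 18 patients in stage 1, 28 in total, continuation on one response (read as at least one), response rates of 5% and 15%.
- No responder in stage 1: (1 − p)^18. At 5%, 0.95^18 = 0.397; at 15%, 0.85^18 = 0.054.
- Exactly one responder in 28 (one in stage 1, none in the next 10): 18·p·(1 − p)^27. At 5%, 18 × 0.05 × 0.95^27 = 0.225; at 15%, 0.034.
- One responder or none at trial end: 0.397 + 0.225 = 0.623 before rounding at 5%; 0.087 at 15%.
- With 1 responder against 27, the smallest two-sided rank-sum p is 2/28 = 0.071.
- Expected responders in 28: 1.4 at 5%, 4.2 at 15%. From the noncentral t distribution with n1 + n2 − 2 df and noncentrality d·√(n1·n2/(n1 + n2)), the detectable difference is 1.57 between-patient SD for 4 against 24, and 1.78 for 3 against 25.

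**2. What the paired data could show.** Paired t-test with n − 1 df and noncentrality d·√n, d being the mean change divided by the SD of the change. Cohort sizes: 9 + 5 = 14 each, or 9 each if the trial stops at 18. To put the result in between-patient SDs, multiply d by √(2(1 − r)), where r is the within-patient correlation (not in the documents, so a range is shown).

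| Pairs | SD of change | r = 0 | r = 0.5 | r = 0.7 |
|---|---|---|---|---|
| 14 | 0.81 | 1.15 | 0.81 | 0.63 |
| 9 | 1.07 | 1.51 | 1.07 | 0.83 |

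With 9 pairs the smallest two-sided signed-rank p is 2/2^9 = 2/512 = 0.004.

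**3. Using the named two-sample test on before and after values.** For 14 pairs and a shift of 0.8 between-patient SD (an assumed value; unpaired results from 20,000 simulations):

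| r | Paired t power | Unpaired t power | Unpaired type I error |
|---|---|---|---|
| 0 | 0.50 | 0.53 | 0.050 |
| 0.5 | 0.79 | 0.55 | 0.008 |
| 0.7 | 0.95 | 0.56 | 0.001 |

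Nothing is lost at zero correlation. With positive correlation the unpaired test becomes conservative and wasteful.

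**4. The biopsy #1 window.** Day -28 to Day -1 is 28 days. Of these, 14 (Day -14 to Day -1) fall on or after the first metformin day, and 13 fall strictly after it.

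**5. How much a late biopsy #1 could dilute the change.** Metformin runs for 14 days before a C1D1 biopsy #2 and 28 days before a C1D15 one. If change builds with days on drug, the share left after a biopsy #1 on Day -10 is 10/14 = 71% and 24/28 = 86%. If it builds with cumulative dose under Table 1, the lead-in total is 3 × 1000 + 4 × 1500 + 7 × 2000 = 23,000 mg, and 14 × 2000 = 28,000 mg follows by C1D15, making 51,000 mg.

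| Biopsy #1 | C1D1: by days | C1D1: by dose | C1D15: by days | C1D15: by dose |
|---|---|---|---|---|
| Day -10 | 71% | 80% | 86% | 91% |
| Day -7 | 50% | 61% | 75% | 82% |
| Day -3 | 21% | 26% | 61% | 67% |

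As a worst case, if every one of 14 pairs lost 25% or 50% of a change set for 80% power, power would fall to 56% or 29%.

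**The case against.** The other side has a fair case.

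- **The biomarker work is labelled hypothesis generating, and other exploratory tests are allowed.** This stands in part: a paired test is not forbidden, and no alpha or decision rests on it. But 10.2 spells out the responder comparisons and leaves out the one analysis that answers a stated objective. Nor can its t-test readily be read as paired, since its contrast is between groups and its non-parametric partner is the rank sum test, not the signed-rank test.
- **The responder tests are not wrong.** Correct. Sections 4.4 and 8.1.3.1 also seek markers that go with response or clinical outcome, and these tests serve that aim. Their weakness is not itself damage to objective 2. The 1.57 and 0.81 figures answer different questions on different scales and should not be read as a ratio.
- **The wording on other factors could cover C1D1 against C1D15.** It could, with a detectable difference of 1.10 between-patient SD for 14 against 14. That still compares patients and not before with after.
- **Biopsy #1 is plainly meant to precede treatment.** It is called baseline and sits under Screening, and the same Day -28 to -1 header covers consent and eligibility, which nobody would do after starting drug. The intent is clear. Yet the only ordering condition written for biopsy #1 is consent, whereas baseline blood in the same section is tied to the start of therapy.
- **The dilution figures rest on an assumed time course.** They do. The day-based and dose-based versions differ, and the documents support neither over the other.

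**Conclusion.** The concern holds. Objective 2 has no prespecified method that matches it, section 10 is silent on the two biopsy #2 exposures, and the written biopsy #1 window overlaps the metformin lead-in on 14 of its 28 days.

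The size is moderate. The primary response-rate analysis is untouched, and the data can still be analysed properly, so what is lost is prespecification. The risk that the named response-based tests yield little is real: at a 5% response rate there is a 62% chance of ending with one responder or none. That figure takes the stage 1 rule as at least one response in 18. The detectable differences assume normal data, two-sided 5%, 80% power and the correlations shown, with every planned pair available. The documents give no basis for estimating how often biopsy #1 would fall on drug, so the window is a gap to close and not a demonstrated bias. The change should be made but is not critical to the trial's main conclusion.

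**What to change.** **In 10.2:** make within-patient change from baseline the main biomarker analysis, by paired t-test or Wilcoxon signed-rank test. For tissue, do it separately in the C1D1 cohort (metformin alone) and the C1D15 cohort (combination). For blood, compare each later time point with baseline. State that it is exploratory, with nominal p-values and no multiplicity claim. Keep the responder comparisons as secondary and descriptive.

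**In 8.1.3.1, 8.1.5.1 and calendar footnote h:** reconcile the biopsy #1 window with the lead-in so that biopsy #1 precedes the first metformin dose, for example by counting the 28 days back from Day -14.

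**Cost:** SAP wording and one window definition, with no added biopsies. Scheduling becomes tighter. Biopsy #1 must follow consent, and 8.1.5.1 also ties consent to the 28 days before C1D1; unless that is re-anchored too, the usable biopsy #1 window shrinks from 28 days to 14. More marker-by-time tests will also produce more chance findings, which is why the exploratory label matters.

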10.3 Evaluation of Response

All patients included in the study must be assessed for response to treatment, even if there are major protocol treatment deviations or if they are ineligible. Each patient will be assigned one of the following categories: 1) complete response, 2) partial response, 3) stable disease, 4) progressive disease, 5) early death from malignant disease, 6) early death from toxicity, 7) early death because of other cause, or 9) unknown (not assessable, insufficient data). [Note: By arbitrary convention, category 9 usually designates the "unknown" status of any type of data in a clinical database.]

All of the patients who met the eligibility criteria (with the possible exception of those who received no study medication) should be included in the main analysis of the response rate. Patients in response categories 4-9 should be considered to have a treatment failure (disease progression). Thus, an incorrect treatment schedule or drug administration does not result in

exclusion from the analysis of the response rate. Precise definitions for categories 4-9 will be protocol specific.

All conclusions should be based on all eligible patients. Subanalyses may then be performed on the basis of a subset of patients, excluding those for whom major protocol deviations have been identified (e.g., early death due to other reasons, early discontinuation of treatment, major protocol violations, etc.). However, these subanalyses may not serve as the basis for drawing conclusions concerning treatment efficacy, and the reasons for excluding patients from the analysis should be clearly reported. The 95% confidence intervals should also be provided.

10.4 Analysis Sets

All subjects who receive any amount of study drug will be included in the evaluation of safety and efficacy.

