1. STUDY SYNOPSIS

| |
|---|
| 
Title of Study: Phase II trial of Nivolumab and Metformin in patients with treatment refractory MSS metastatic Colorectal Cancer
 |
| 
Study Centers: Emory University Winship Cancer Institute
 |
| 
Study Phase: Phase II
 |
| 
Objectives:
 
Primary Objective:
 
▪ The primary endpoint of this study is to Evaluate the effect of metformin in combination with nivolumab on the overall response rate (ORR) (Primary Objective) as assessed by RECIST.1.1 
Secondary Objectives:
 
▪ To determine the effect of the metformin and nivolumab combination on clinical (PFS, OS) outcomes and biochemical (CEA) response.▪ To compare the effect metformin and nivolumab combination on immune and metabolic biomarkers in the tumor microenvironment and systemic circulation (pre and post treatment paired biopsies required). |
| 
Trial Design/Methodology: Single arm phase II study. 28 patients with previously treated (previously treated with fluoropyrimidine, oxaliplatin, irinotecan and EGFR inhibitor – if RAS wildtype) metastatic CRC will be started on metformin and nivolumab combination.
 
Treatment
 
1. Patients will start taking metformin 500 mg po BID for 3 days, then 500 mg am and 1000 mg pm for 4 days, then 1000 mg po bid for 1 week. Patients of the study will get paired biopsies as outlined in study calendar.2. If a patient cannot tolerate metformin 1000 mg po BID the patient will resume the metformin dose which was tolerable3. After 2 weeks of metformin only therapy (lead-in period) patients will start nivolumab 480 mg IV q4 weeks and continue metformin 1000 mg PO BID (or the tolerated dose of Metformin).4. Restaging scans will be performed at the end of cycle 2, then every 8 weeks for 2 years.5. Correlative assays will include- immune profiling of TILs and circulating lymphocytes, plasma cytokine levels and metabolic biomarkers. These will be performed at baseline at baseline, cycle 1 day 1, cycle 1 day 15, Cycle 3 Day 1 and at progression 
Treatment regimen and trial diagram:
 |

Main criteria for exclusion:

- MSI status
- Autoimmune conditions that may require systemic steroids or other immunosuppressive treatments
- Pregnancy or breast feeding

Investigational product and administration:

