Metformin is a biguanide and decreases liver glucose production and increases insulin sensitivity. It is the first line therapy and most commonly prescribed antidiabetic agent for diabetes mellitus type II. It has favorable safety profile, weight neutral effects, low risk of hypoglycemia and low cost. [14] Immediate release (IR) and extended release formulations (ER) exist and extended release formulation provides better tolerability especially lower gastrointestinal adverse events as well as improved patient adherence. ER formulation provides gradual release of the drug into upper GI tract although it provides similar drug exposure at the same daily total dose as immediate release formulation. [14] Maximum plasma concentration of IR Metformin is reached at 2-3 hours and 7 hours for ER Metformin. [15] ER tablets cannot be crushed or chewed and should be swallowed whole in order to maintain slow drug release. The most common adverse events were reported as following in a 16-week, randomized, double-blind, placebo-controlled study in patients with type II diabetes: upper respiratory tract

infection (15%), diarrhea (12.9%), nausea/vomiting (8.2%), musculoskeletal pain (7.6%), headache (7.1%), influenza (6.6%), dyspepsia/heartburn (5.3%), abdominal pain (5.1%), sinus abnormality (3.7%), dizziness (3.4%), hypertension (3.1%), urinary tract infection (3.1%). That particular study included 5 different treatment regimens including Metformin ER 1000 mg po twice daily.

Please refer to the Investigator's Brochure for additional information for preclinical activity, toxicology and potential adverse effects.

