6. TREATMENT PLAN

6.1.1 Agent Administration

Treatment will be administered on an outpatient basis. Reported adverse events and potential risks are described in Section 7. Appropriate dose modifications are described in Section 6. No investigational or commercial agents or therapies other than those described below may be administered with the intent to treat the patient's malignancy.

Table 1: Cycle 1 only (Day -14 through 28) Lead-in period

| Regimen Description | | | | | |
|----------------------------|-------------------------------------|-------------|--------------|-----------------|---------------------|
| Agent | Premedications ; Precautions | Dose | Route | Schedule | Cycle Length |
| | | | | | 42 days |

| | | | | | |
|------------|----------------|-----------------------------------|----|------------------------------------|--|
| Metformin | Take with food | 500 mg tablet am, 500 mg pm | PO | Twice daily D-14 through -12 | |
| Metformin | Take with food | 500 mg tablet am, 1000 mg pm | PO | Twice daily D -11 through -8 | |
| Metformin | Take with food | 1000 mg tablet am, 1000 mg pm | PO | Twice daily D -7 through -1 | |
| Metformin* | Take with food | 1000 mg tablet and, 1000 mg pm | PO | Twice daily, D1-28 | |

*If subject cannot tolerate 1000 mg po twice daily, will resume the highest tolerated dose of Metformin.

NOTE: The patient will be requested to maintain a medication diary of each dose of medication (Metformin). The medication diary ([Appendix B](#)) will be returned to clinic staff at the end of each course. Patients with diabetes mellitus will be requested to keep a blood glucose log for the first 4 weeks of the trial ([Appendix C](#))

Table 2: Cycle 2 and subsequent cycles (28 days)

| Regimen Description | | | | | |
|---------------------|------------------------------|------|-------|----------|--------------|
| Agent | Premedications ; Precautions | Dose | Route | Schedule | Cycle Length |

| | | | | | |
|------------|--|--------------------------------|--------------------|--------------------|-------------------|
| Nivolumab | Premedicate with Acetaminophen 650 mg po once prior to Nivolumab, optional | 480 mg | IV over 30 minutes | Day 1 | 28 days (4 weeks) |
| Metformin* | Take with food | 1000 mg tablet and, 1000 mg pm | PO | Twice daily, D1-28 | |

* If subject cannot tolerate 1000 mg po twice daily during Cycle 1, subject will continue the maximum tolerated dose of Metformin as in cycle 1 for the subsequent cycles.

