6.12 Subject Replacement Strategy

Patients who do not complete the intended course of therapy due to reasons other than toxicity, clinical or radiographic disease progression will be considered as in-evaluable for the primary endpoint and will be replaced. Subject are not able to tolerate metformin despite 2 dose reductions in the first 2 weeks of the trial (Metformin only phase) will be considered inevaluable and replaced.

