8.1.5.4 Cycle 1 Day -7 phone call

- Metformin
- Review of adverse events, dosing compliance and concomitant medication (by clinical trial coordinator via phone call)

8.1.5.5 Cycle 1 Day 1

- Record concomitant medications
- Vitals (temperature, HR, BP and RR)
- History and physical exam, pill diary and pill count, blood glucose log for diabetic patients
- ECOG performance status
- Toxicity assessment
- Laboratory Assessments
 - Hematology hemoglobin, hematocrit, red blood cell count, white blood cell count with differential and platelet count
 - Chemistry sodium, potassium, chloride, bicarbonate, magnesium, calcium, phosphorus, blood urea nitrogen, creatinine, glucose (random), total bilirubin, LDH, total protein, ALP, ALT, AST, and albumin
- Blood sample 20 cc for correlative work
- **Subject# 1-9, 19-23** (14 patients in total) will get biopsy#2 of paired biopsy (same day or up to 5 days later)
- Continue metformin
- Nivolumab will be started after biopsy#2 (same day or up to 5 days later).
- Nivolumab 480 mg will be administered as a 30-minute IV infusion in the infusion center. Given the variability of infusion pumps, a window of -5 minutes and +10 minutes is permitted (i.e., infusion time is 30 minutes: -5 min/+10 min).

8.1.5.6 Cycle 1 Day 15

- Record concomitant medications
- Vitals (temperature, HR, BP and RR)
- History and physical exam, pill diary and pill count, blood glucose log for diabetic patients
- ECOG performance status

- Toxicity assessment
- Laboratory Assessments
 - Hematology hemoglobin, hematocrit, red blood cell count, white blood cell count with differential and platelet count
 - Chemistry sodium, potassium, chloride, bicarbonate, magnesium, calcium, phosphorus, blood urea nitrogen, creatinine, glucose (random), total bilirubin, LDH, total protein, ALP, ALT, AST, and albumin
 - Tumor marker – CEA
- Blood sample 20 cc for correlative work
- The second half of the patients **Subject #10-18, 24-28** (14 patients in total) will get biopsy#2 of paired biopsy (same day or up to 5 days later)
- Continue metformin

8.1.5.7 Cycle 2 Day 1

- Record concomitant medications
- Vitals (temperature, HR, BP and RR)
- History and physical exam, pill diary and pill count
- ECOG performance status
- Toxicity assessment
- Laboratory Assessments
 - Hematology hemoglobin, hematocrit, red blood cell count, white blood cell count with differential and platelet count

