10.6 Safety Analysis

10.6.1 Adverse Events

Adverse events will be classified using MedDRA System Organ Classes and Preferred Terms. Furthermore, SAEs, AEs with a severity grade of 3 or above using NCI CTCAE version 4.0, AEs deemed related to study drug, AEs leading to discontinuation of study drug, and AEs leading to death will also be summarized in preferred term by system organ class and listed on an individual subject basis.

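### Safety is tabulated only as pooled any-drug percentages, so events starting on metformin alone cannot be separated, as rates, from events after nivolumab starts

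*Combined protocol and SAP*

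**What the plan says.** - **Analysis set (10.4).** One set serves safety and efficacy: "All subjects who receive any amount of study drug will be included in the evaluation of safety and efficacy". Section 9.1 lists both nivolumab and metformin under investigational product, so metformin alone qualifies.
- **Summary measure (10.2).** "Toxicities will be presented as worst toxicity per patient and will be reported as percent toxicity".
- **Tables (10.6.1 to 10.6.3).** Events are classified by MedDRA term, and "AEs deemed related to study drug, AEs leading to discontinuation of study drug, and AEs leading to death will also be summarized". Laboratory worst grades and dose modifications are also summarised. None of these is split by period, by drug or by nivolumab exposure.
- **Lead-in.** The synopsis states: "After 2 weeks of metformin only therapy (lead-in period) patients will start nivolumab 480 mg IV q4 weeks". In the visit schedule (8.1.5.5, Cycle 1 Day 1), "Nivolumab will be started after biopsy#2 (same day or up to 5 days later"). The heading in 6.1.1 differs: "Table 1: Cycle 1 only (Day -14 through 28) Lead-in period", and that table lists metformin only.
- **Collection.** Non-serious events are collected from the first study drug (8.2.2.1), so lead-in events enter the database.
- **Leaving before nivolumab.** Section 6.12 replaces a patient described as "Subject are not able to tolerate metformin despite 2 dose reductions in the first 2 weeks of the trial (Metformin only phase"). Section 8.1.3.1 replaces anyone who has the first biopsy and refuses the second. For subjects 1-9 and 19-23 the second biopsy comes before the first nivolumab dose.

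**The concern.** The regimen has two phases with different exposures, but the plan yields one percentage per event term. Diarrhoea shows the difficulty. Section 4.2.2 quotes it at 12.9% in a metformin study, and section 4.2.1 lists diarrhoea and colitis among grade 3 or 4 events on nivolumab. A patient with grade 2 diarrhoea on metformin alone and a new grade 2 episode after nivolumab counts once, and nothing in the table shows that the second episode followed nivolumab.

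Attribution does not fill the gap. Table 6 (8.3.2) records one yes/no judgement for the investigational product(s) together, and 10.6.1 summarises relatedness to study drug without naming which. The laboratory table in 10.6.2 uses change from baseline without saying whether baseline precedes metformin or nivolumab.

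At stake is whether someone planning a later trial of the two drugs can read from the report how often an event arose once both were being given.

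**Working it through.** The plan states no toxicity rate, threshold or safety power, so there is no figure to reproduce. The two effects can only be illustrated.

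**Inputs from the documents.** Planned number 28 (10.1). Metformin diarrhoea 12.9%, from a 16-week diabetes study with five regimens (4.2.2).

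**Inputs assumed.** Patients replaced before nivolumab: 2, 3 or 5, on top of 28 exposed. Rate among the exposed of an event that arises only after nivolumab: 20%. Diarrhoea rate after nivolumab starts: 15%. Share of the 12.9% that occurs in the lead-in: 25% to 100%.

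**Step 1: unexposed patients in the denominator.** If k unexposed patients have no such event, the pooled rate is 0.20 × 28 / (28 + k).

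| k | Pooled rate |
|---|---|
| 2 | 5.6 / 30 = 18.7% |
| 3 | 5.6 / 31 = 18.1% |
| 5 | 5.6 / 33 = 17.0% |

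The shift is 1.3 to 3.0 percentage points downward.

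**Step 2: lead-in events in the numerator.** The expected number of 28 patients with lead-in diarrhoea is 28 × 0.129 = 3.6 at the upper end and 0.25 × 3.6 = 0.9 at the lower end. If lead-in and later diarrhoea are independent, the any-time rate is 1 − (1 − 0.129q)(1 − 0.15), where q is the assumed share:

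- q = 0.25: 1 − 0.96775 × 0.85 = 17.7%
- q = 1: 1 − 0.871 × 0.85 = 26.0%

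Independence is generous. Metformin continues throughout, so patients with lead-in diarrhoea may well have it later too. If all of them did, the pooled rate would stay at 15%, because 12.9% is below 15%. The two results are therefore upper values, provided lead-in diarrhoea does not make later diarrhoea less likely. The upper end also places all of a 16-week rate in a two-week titrated lead-in.

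**Step 3: net effect.** Step 1 lowers the pooled percentage and step 2 raises it. For gastrointestinal terms both can act at once. Since the documents give no dropout count and no lead-in event rate, the sign of the net effect for a given term cannot be determined.

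**The case against.** The strongest reply is that nothing here is an error. The lead-in is part of Cycle 1, metformin is investigational product, and counting everyone exposed is the ordinary conservative safety set. That stands. A reader might infer that section 10.4 defines the wrong population, or that the plan misreports the toxicity of the combination. The documents support neither: the plan never labels its percentages as rates for the combination.

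A reader might also infer that immune-related rates are diluted and gastrointestinal rates inflated. Section 10.6 plans no immune-related rate, and step 3 shows that the net direction is unknown.

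Three further replies carry weight:

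- Safety is not among the objectives in 3.1 and 3.2, section 10.2 calls its analyses hypothesis generating, and no decision rule in section 10 uses a toxicity percentage. This limits the importance of the point.
- Event start and stop dates are recorded (8.3.2). Serious, grade 3 or higher and related events, and those leading to discontinuation or death, are listed by subject (10.6.1), as are laboratory values of grade 3 or higher (10.6.2). It would be too strong to say that a reader cannot tell early from late events at all. But listings give no period-specific rate, help only if they show onset, and omit lower-grade events judged unrelated.
- The denominator shift is small against sampling error: the exact 95% interval for 6/28 is about 8% to 41%. The routes to it are also narrow. The intolerance rule is conditional, and full metformin dose begins only on Day -7, so two reductions from it would have to fall within a week. Refusal of the second biopsy before nivolumab concerns only the 14 patients biopsied at Cycle 1 Day 1.

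**Conclusion.** The point holds as a gap in tabulation. As planned, the report cannot give the rate of events starting on metformin alone or the rate from the first nivolumab dose among patients who received it. Mixing the periods matters more than the denominator.

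The illustrated sizes are 1.3 to 3.0 points of dilution on a 20% rate, and up to about 3 to 11 points of inflation on a 15% rate (17.7% − 15% and 26.0% − 15%). All rest on assumed dropout numbers and event rates, and the second also on independence, so they show scale and do not predict a bias. The primary endpoint is unaffected. This is an inexpensive improvement to reporting that uses data already collected.

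**What to change.** Keep the pooled any-drug table as the overall safety table. Add two tables, each with its own denominator, and split the 10.6.2 laboratory grades in the same way:

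1. **Metformin-only period.** All patients who took metformin; events with onset before the first nivolumab dose.
2. **From the first nivolumab dose.** Patients with at least one nivolumab dose; new or worsened events and, shown separately, events ongoing from the lead-in. Showing only new or worsened events would hide metformin toxicity that persists on the combination.

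Define the boundary by the actual date of the first nivolumab dose, because the visit schedule lets it fall after Day 1. State which baseline 10.6.2 uses for each period. Report the number of patients never given nivolumab, and state that patients replaced under 6.12 stay in the safety set; its second sentence calls them inevaluable without saying for what.

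Before the periods can be defined, Table 1 in 6.1.1, which labels Day -14 through 28 as lead-in and lists only metformin, must be reconciled with the synopsis and with 8.1.5.5. This review takes no position on which is right.

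The cost is a few sentences in section 10 and additional tables with small counts in each. No new data or patients are needed: onset dates are recorded, and adverse events are already reviewed at Day -7 and Cycle 1 Day 1.
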